3.4.3. Rationale for Extended Infusion or Re-Dosing of Andexanet

In this study, there is potential for patients to require additional andexanet treatment beyond what is initially stipulated (bolus + 120-minute infusion). For example, unpredictable events during surgery may prolong the duration of surgery. Based on clinical judgement of procedural or patient factors, the treating physician may determine that the infusion should additionally extend to the immediate postoperative period. In addition, a surgical patient may bleed after completion of surgery. Therefore, extended andexanet infusions (to address longer surgeries) and re-dosing of andexanet (for post-surgical bleeding events) will be implemented in the protocol.

A low-dose continuous infusion (4 mg/min) for up to an additional 4 hours was selected as the regimen to use for extended infusions, whereas a low-dose bolus (400 mg) plus continuous infusion (4 mg/min for 120 minutes) will be used for re-dosing. The rationale for these dosing levels is based on the premise that the amount of reversal agent required to neutralize an FXa inhibitor diminishes as the inhibitor is eliminated over time.

Investigators will be required to document in the electronic case report form (eCRF) the clinical justification for why subjects require extended infusion of andexanet or additional dosing of andexanet during surgery. Please refer to [Appendix A](#) for the timing of extended infusion or re-dosing of andexanet in surgical patients. The decision criteria for extended duration of dosing or re-dosing during surgery are outlined in Section [6.2](#).

Re-dosing Criteria:

Factors that may determine if re-dosing is appropriate include the treating surgeon's consideration of patient factors, such as degree of visible bleeding, hemodynamic stability, need for hemostatic support products, or to avoid reoperation to control bleeding. The Investigator may also consider clinical suspicion that the patient has levels of FXa inhibition sufficient to contribute to bleeding based on patient factors such as time from last FXa inhibitor dose, safety assessments required by the protocol or routine care and renal function. Additionally, the need for re-operation to control bleeding may be considered reason re-dose to avoid the additional procedure.

3.5. Safety Plan and Monitoring

The study will be conducted in patients who are hospitalized. As such, treatment with andexanet and subsequent monitoring will be done in a medical setting. It is expected that patients requiring urgent surgery will remain hospitalized for at least 12 hours, the timeframe for the primary efficacy evaluations. During the first 12-hour period (Study Day 1), AEs, vital signs, physical examinations, and laboratory testing will be performed as indicated in [Appendix A](#) to monitor safety. Survival status will be ascertained on Study Day 30, and, if applicable, cause of death will be recorded. Antibody samples will be taken at baseline and Day 30 to assess immunogenicity against andexanet, FX, FXa, nAb, and HCPs.

Of the 352 patients, 9.7% of patients with acute major bleeding in ANNEXA-4 experienced protocol-defined, adjudicated TEs that occurred within 30 days of andexanet treatment. While the attributability of these events to andexanet is uncertain, it is significantly possible that they will occur in the current study, given the anticipated enrolled population, for which reversal of anticoagulation may expose the underlying risk of TEs, and andexanet's known effects on coagulation biomarkers such as D-dimer, F1+2, and TFPI. In this study, patients with TEs within 30 days of Screening, those with a history of hypercoagulable states, and those who received procoagulant products within 7 days of Screening will not be eligible for the study due to their much greater risk for TEs in general and following anticoagulation reversal. In this study, TEs will be considered AEs of special interest (AESIs) and will be reported within 24 hours to the Sponsor. Thrombotic events, both suspected and confirmed by adjudication, will be tracked as safety endpoints for the study. To mitigate the risk of TEs, Investigators are encouraged to consider resumption of an anti-thrombotic agent (preferably oral) as soon as it is clinically appropriate. Additional clinical precautions to mitigate thrombotic risk in postoperative care such as early mobilization, sequential compression devices or other routine measures should also be strongly considered.

Prior and ongoing clinical studies have identified infusion reactions of mild or moderate intensity as an AE related to administration of andexanet (described in Section [1.4.5](#)). Patients in this study will receive andexanet in an inpatient, monitored setting under medical supervision and immediate access to resuscitative measures. Infusion reactions observed in prior and ongoing studies have had their onset during the infusion itself.

Whether or not patients have been discharged from the hospital, they will undergo the Study Day 2, Study Day 3, and Follow-up Day 30 visits to assess safety. Due to the theoretical possibility of antibody formation to andexanet, FX, FXa, or HCPs, antibody testing will be performed at baseline and at the Study Day 30 visit.

The independent EAC, in addition to adjudicating the primary endpoint, will also adjudicate all TEs, deaths, and all post-surgical bleeding events using pre-defined criteria as described in their charter. A DSMB will review all safety data on a schedule described in the DSMB charter. In

addition, safety data will be reviewed by the Sponsor at an ongoing basis. Guidelines for the management of specific AEs are provided in Section 8.0.

3.6. Benefit and Risk Assessment

Factor Xa inhibitors are a significant therapeutic advance in several indications. However, a significant risk of anticoagulation with FXa inhibitors is the potential for uncontrolled bleeding. In the case of urgent surgery, a delay in surgical treatment necessary to sufficiently diminish anti-coagulant concentrations could potentially result in deleterious clinical consequences. While andexanet is approved for the management of acute major bleeding related to FXa inhibitor use, it is unknown whether it is efficacious and safe in patients who require urgent surgery in the setting of recent use of an FXa inhibitor. Andexanet may be beneficial in reversing anticoagulation due to FXa inhibition and, thus, facilitating normal hemostasis during the surgical procedure. In addition to any personal benefit to individual patients, there is a potential benefit to all current and future patients treated with andexanet (and, more generally, all patients taking FXa inhibitors) from the insights gained through this clinical study.

The risks of study participation involve the risk of experiencing an AE related to andexanet or to the study procedures. To date, no major safety issues directly attributable to andexanet have definitively emerged in clinical studies. However, whenever chronic anticoagulation is reversed in patients with an indication to receive it, the risk of thromboembolic events is increased. Additionally, surgical intervention can also increase thromboembolic risk. This risk must be balanced against the potential for new or worsening bleeding related to the surgery. The PD effect of andexanet is short. Therefore, shortly after the infusion is discontinued and once the potential for bleeding is minimized, it will be possible to return the patient to a therapeutically anticoagulated state as needed. It is recommended that the Investigator carefully weigh the risk of new bleeding against the risk of thrombosis when considering when to resume anticoagulation for the patient.

Procedural risks inherent to the urgent surgical procedure itself would vary based on the procedure type and individual patient risk factors, and should be additionally communicated to the patient by the treating physician.

The safety monitoring plan for this study is robust (see Section 3.5), including treatment of patients in a hospital setting, an approximate 30-day safety follow-up, ongoing review of safety data by the Sponsor and independent safety reviews by the DSMB as well as adjudication of TEs, deaths, hemostatic efficacy, and post-surgical bleeding events by the EAC.

Based on the above considerations, the potential risks to patients in this study are justifiable. Patients or their legally authorized representative will be consented as to the potential risks and will be required to sign an informed consent form (ICF), documenting their understanding of these risks and willingness to participate in the study.

4.0 SELECTION OF STUDY POPULATION AND CRITERIA FOR WITHDRAWAL

4.1. Inclusion Criteria

All of the following criteria must be met for the patient to be eligible to participate in the study:

1. Either the patient or his or her medical proxy (or legal designee) has given written informed consent prior to Screening.
2. Age ≥ 18 and < 85 years old.
3. Requires urgent surgical intervention that must occur within 12 hours of consent, for which reversal of anti-fXa activity is judged necessary.
4. Received 1 of the following FXa inhibitors apixaban, rivaroxaban, edoxaban, or enoxaparin (dose of enoxaparin ≥ 1 mg/kg/d) within 15 hours prior to start of surgery. If the time from the last dose is unknown, or greater than 15 hours and a local anti-fXa activity level obtained within 2 hours prior to consent is > 100 ng/mL (> 0.5 IU/mL for enoxaparin), the patient may be enrolled.
5. Have a negative pregnancy test documented prior to enrollment (for women of childbearing potential).
6. Willingness to use medically acceptable methods of contraception through 30 days following study drug dose (for female and male patients who are fertile).

4.2. Exclusion Criteria

If a patient meets any of the following criteria, he or she is *not* eligible to participate:

1. Surgery for which the risk of clinically meaningful uncontrolled or unmanageable bleeding is low.
2. Acute life-threatening bleeding (ISTH criteria [7]) at the time of Screening:
 - a. The patient has acute-overt bleeding that is potentially life-threatening, e.g., with signs or symptoms of hemodynamic compromise, such as severe hypotension, poor skin perfusion, mental confusion, low urine output that cannot be otherwise explained.
 - b. The patient has overt bleeding associated with a fall in hemoglobin level by ≥ 2 g/dL, OR, a hemoglobin ≤ 8 g/dL if no baseline hemoglobin is available.
 - c. The patient has acute bleeding in a critical area or organ, such as pericardial, intracranial, or intraspinal.
3. Any surgical procedure requiring cardiopulmonary bypass, an intra-aortic catheter, or the intraoperative use of systemic, intravascular, unfractionated heparin.

4. Primary procedure being considered for efficacy evaluation is a non-surgical interventional procedure (e.g., skin biopsy, lumbar puncture, cardiac catheterization, endoscopic retrograde cholangio-pancreatography).
5. Expected survival of < 1 month due to comorbidity.
6. Known “Do Not Resuscitate” order or similar advanced directive.
7. The patient has a recent history (within 30 days prior to Screening) of a diagnosed TE as follows: VTE (including DVT, PE, intracardiac thrombus); MI (including asymptomatic troponin elevations); disseminated intravascular coagulation (DIC); acute traumatic coagulopathy; cerebrovascular accident; transient ischemic attack; unstable angina pectoris hospitalization; or severe peripheral vascular disease (see [Appendix B](#) for DIC scoring algorithm).
8. Acute decompensated heart failure or cardiogenic shock at the time of screening (see [Appendix C](#) for cardiogenic shock definition)
9. The patient has severe sepsis or septic or hemorrhagic shock at the time of Screening (see definition in Appendix C).
10. The patient has heparin-induced thrombocytopenia (with or without thrombosis).
11. Inherited coagulopathy (e.g., anti-phospholipid antibody syndrome, protein C/S deficiency, Factor V Leiden).
12. Platelet count < 80,000/ μ L at the time of Screening.
13. Last dose of apixaban < 2.5 mg, rivaroxaban < 10 mg, edoxaban < 30 mg, enoxaparin < 40 mg.
14. The patient is pregnant or a lactating female.
15. The patient has received any of the following drugs or blood products within 7 days of enrollment:
 - Vitamin K antagonists (e.g., warfarin).
 - Dabigatran.
 - Prothrombin complex concentrate products (PCC, e.g., Kcentra[®]), recombinant factor VIIa (rFVIIa) (e.g., NovoSeven[®]).
 - Whole blood, plasma fractions.
 - Note: Administration of tranexamic acid (TXA), platelets, or packed red blood cells (PRBCs) is not an exclusion criterion.
16. The patient was treated with an investigational drug < 30 days prior to Screening.
17. Prior treatment with andexanet.

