3.4.2.2. Management of Patients Taking FXa Inhibitors Requiring Urgent Surgery

There is currently no specific or approved treatment option for patients requiring reversal of FXa inhibition for urgent surgery. In general, if a patient is anticoagulated and requires surgery, the primary approach to managing this clinical scenario is to delay the procedure to facilitate elimination of the FXa inhibitor. Current practice is to weigh the risk of proceeding with the surgery, with the attendant prospect of hemorrhage, against the risk of delaying the procedure to achieve lower anti FXa activity levels. Inappropriate surgical delay could potentially result in serious or life-threatening clinical complications such as progressive contamination of the abdominal cavity (e.g., perforation of duodenal ulcer, perforated diverticulitis) or inflamed organ perforation (appendicitis). Postponement of treatment may also result in soft tissue infection progression, especially when diabetic comorbidity is present (e.g., abscess, necrotizing fasciitis). Delayed operative management for ischemic conditions could result in necrosis, prolonged postoperative management, and mortality.

Of relevance, additional studies have reported clinical outcomes such as mortality, complications, and increased use of health care resources associated with delays in surgical intervention [12]. In a recent cohort study evaluating patients with perforated peptic ulcers, every hour of delay from admission to surgery was associated with an adjusted 2.4% decreased probability of survival compared with the previous hour [13]. Conditions such as cholecystitis progressing to perforation, or ischemic consequences for small bowel obstruction are additional examples of surgical delay leading to clinical deterioration and requirements for more extensive operative management. Patients taking FXa inhibitors may experience delays in orthopedic procedures such as hip fracture repair, a procedure in which delay is proven to have adverse

clinical consequences [14]. While there is some variability (at least partially procedure-dependent) in the magnitude of delay associated with increased morbidity and mortality, it is generally accepted that the delay itself meaningfully increases the risk of a negative outcome.

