3.5. Safety Plan and Monitoring

The study will be conducted in patients who are hospitalized. As such, treatment with andexanet and subsequent monitoring will be done in a medical setting. It is expected that patients requiring urgent surgery will remain hospitalized for at least 12 hours, the timeframe for the primary efficacy evaluations. During the first 12-hour period (Study Day 1), AEs, vital signs, physical examinations, and laboratory testing will be performed as indicated in Appendix A to monitor safety. Enrolled patients will be closely monitored during the period where they are most vulnerable and the risk of thrombosis is highest.

Survival status will be ascertained on Study Day 30, and, if applicable, cause of death will be recorded. Antibody samples will be taken at baseline and Day 30 to assess immunogenicity against andexanet, FX, FXa, nAb, and HCPs. Due to the ongoing severe acute respiratory syndrome coronavirus 2 (SARS-CoV-2/COVID-19) pandemic, the Day 30 visit may be conducted by phone; considerations for laboratory samples are discussed in Section [3.7](#).

Of the 352 patients, 9.7% of patients with acute major bleeding in ANNEXA-4 experienced protocol-defined, adjudicated TEs that occurred within 30 days of andexanet treatment. While the attributability of these events to andexanet is uncertain, it is significantly possible that they will occur in the current study, given the anticipated enrolled population, for which reversal of anticoagulation may expose the underlying risk of TEs, and andexanet's known effects on coagulation biomarkers such as D-dimer, F1+2, and TFPI. In this study, patients with TEs within 30 days of Screening, those with a history of hypercoagulable states, and those who received procoagulant products within 7 days of Screening will not be eligible for the study due to their much greater risk for TEs in general and following anticoagulation reversal. In this study, TEs will be considered AEs of special interest (AESIs) and will be reported within 24 hours to the

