4.2. Exclusion Criteria

If a patient meets any of the following criteria, he or she is *not* eligible to participate:

1. Surgery for which the risk of clinically meaningful uncontrolled or unmanageable bleeding is low.
2. Acute life-threatening bleeding (ISTH criteria [32]) at the time of Screening:
 - a. The patient has acute-overt bleeding that is potentially life-threatening, e.g., with signs or symptoms of hemodynamic compromise, such as severe hypotension, poor skin perfusion, mental confusion, low urine output that cannot be otherwise explained.
 - b. The patient has overt bleeding associated with a fall in hemoglobin level by ≥ 2 g/dL, OR, a hemoglobin ≤ 8 g/dL if no baseline hemoglobin is available.
 - c. The patient has acute bleeding in a critical area or organ, such as pericardial, intracranial, or intraspinal.

3. Any surgical procedure that involves the intraoperative use of systemic, intravascular, unfractionated heparin.
4. Primary procedure being considered for efficacy evaluation is a non-surgical interventional procedure (e.g., skin biopsy, lumbar puncture, cardiac catheterization, endoscopic retrograde cholangio-pancreatography).
5. Expected survival of < 1 month due to comorbidity.
6. Known “Do Not Resuscitate” order or similar advanced directive.
7. The patient has a recent history (within 30 days prior to Screening) of a diagnosed TE as follows: VTE (including DVT, PE, intracardiac thrombus); MI (including asymptomatic troponin elevations); disseminated intravascular coagulation (DIC); acute traumatic coagulopathy; cerebrovascular accident; transient ischemic attack; unstable angina pectoris hospitalization; or severe peripheral vascular disease (see [Appendix B](#) for DIC scoring algorithm).
8. Acute decompensated heart failure or cardiogenic shock at the time of screening (see [Appendix C](#) for cardiogenic shock definition).
9. The patient has sepsis or septic or hemorrhagic shock at the time of Screening (see definition in Appendix C).
10. The patient has heparin-induced thrombocytopenia (with or without thrombosis).
11. Inherited coagulopathy (e.g., anti-phospholipid antibody syndrome, protein C/S deficiency, Factor V Leiden) at time of Screening.
12. Platelet count < 80,000/ μ L at the time of Screening.
13. Last dose of apixaban < 2.5 mg, rivaroxaban < 10 mg, edoxaban < 30 mg, enoxaparin < 40 mg.
14. The patient is pregnant or a lactating female.

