8.2. Thrombotic Events

Patients will be monitored carefully for signs and symptoms of TEs (i.e., strokes, transient ischemic attacks, MIs, DVTs, PEs, arterial systemic embolisms) throughout the course of the study. Should a diagnosis of a TE be considered, it is expected that an appropriate evaluation will be performed (e.g., head computed tomography [CT]/magnetic resonance imaging [MRI], electrocardiogram [ECG]/cardiac enzymes, lower extremity ultrasound, pulmonary vascular imaging). Investigators are requested to consult the guidance listed in [Appendix E](#) when considering whether an event should be considered a TE and therefore be submitted for adjudication. All events submitted for adjudication will be formally considered a suspected TE. Both suspected TEs and TEs confirmed by adjudication will be monitored as safety endpoints.

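### Section 3.5 says patients with a thrombotic event in the last 30 days are ineligible, but exclusion 7 omits arterial systemic embolism, which the protocol itself counts as a thrombotic event

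*Protocol*

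**What the plan says.** The references are to the Amendment 2 text. The Amendment 1 text in the same file has the same list in exclusion 7 and the same statement in Section 3.5.

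- **Section 3.5** says that "patients with TEs within 30 days of Screening, those with a history of hypercoagulable states" and recent recipients of procoagulant products "will not be eligible for the study due to their much greater risk for TEs in general and following anticoagulation reversal". It carves out no type of TE.
- **Section 4.2, exclusion 7** puts this into the entry criteria: "The patient has a recent history (within 30 days prior to Screening) of a diagnosed TE as follows". The list runs from venous thromboembolism to its last items, "unstable angina pectoris hospitalization; or severe peripheral vascular disease". It has no wording that marks the items as examples and no catch-all. The synopsis has the same list.
- **Section 8.2** states what the protocol means by a TE: "strokes, transient ischemic attacks, MIs, DVTs, PEs, arterial systemic embolisms". **Appendix E** gives arterial systemic embolism its own adjudication definition.
- **Section 10.1.7** has the investigator decide eligibility against the inclusion and exclusion criteria, with no exceptions or waivers.
- **Section 3.6** points to the safety plan of Section 3.5 and, on the considerations it sets out, judges the risks to patients justifiable.
- **Sections 11.3.2 and 11.7** report TEs within 30 days of enrollment in all enrolled patients given any andexanet. Section 3.7 names TEs at 30 days as a key safety parameter.

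**The concern.** Section 3.5 describes a safeguard that covers recent TEs of any type. The criterion that has to deliver it leaves out one of the six types the protocol recognises. Sites work from the criteria, so the narrower rule is the one that operates.

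Two things follow. First, patients whom the protocol itself places at markedly raised thrombotic risk could be given a reversal agent, while the benefit-risk section reads as if they were kept out. Second, in a single-arm study they would enter the 30-day TE summary, and a reader of Section 3.5 would assume they were not there. The earlier embolism would not itself be counted as an event; the patient would join the denominator with a higher risk.

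**Working it through.** **Step 1. Match the TE types to exclusion 7.**

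| TE type (Section 8.2) | Item in exclusion 7 |
|---|---|
| Stroke | Cerebrovascular accident |
| Transient ischemic attack | Transient ischemic attack |
| Myocardial infarction | Myocardial infarction |
| Deep vein thrombosis | Venous thromboembolism |
| Pulmonary embolism | Venous thromboembolism |
| Arterial systemic embolism | None |

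Five of six are covered. Exclusion 7 also lists conditions outside Section 8.2: disseminated intravascular coagulation, acute traumatic coagulopathy, hospitalization for unstable angina and severe peripheral vascular disease. The two lists were evidently not aligned with each other.

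**Step 2. Look for another criterion that closes the gap.**

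- An embolus to the brain is caught as a cerebrovascular accident or transient ischemic attack, and one to the coronary arteries as myocardial infarction.
- Intracardiac thrombus is listed, under venous thromboembolism. That catches a diagnosed thrombus in the heart, not an embolus found in a systemic artery.
- Severe peripheral vascular disease may catch some limb emboli, but the protocol does not define it. Appendix E treats arterial systemic embolism as an abrupt occlusion with no other likely mechanism, which is a different thing from established vascular disease.
- Exclusion 3 removes operations that use systemic heparin. It works on other grounds and does not reach a patient whose embolism was some days ago and who now needs an unrelated operation.
- No other exclusion names arterial embolism.

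What remains is non-cerebral, non-coronary arterial embolism: visceral, and limb where the peripheral vascular item does not apply.

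**Step 3. Bound the effect on the TE rate.**

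The only TE rate the protocol gives comes from its earlier study in acute major bleeding (Section 1.4.7): 34/352 = 9.66%, stated as 9.7%. Planned enrollment is about 100 (Section 11.6), so one event is about 1 percentage point.

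Let k of 100 treated patients have a recent arterial embolism with 30-day TE risk r, and let the rest have 9.66%. Neither k nor r is in the documents. As assumptions, take k from 1 to 5 and r from 20% to 50%.

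Expected rate = [(100 − k) × 0.0966 + k × r] / 100

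- k = 1, r = 0.20: (99 × 0.0966 + 0.20)/100 = (9.56 + 0.20)/100 = 9.76%
- k = 5, r = 0.50: (95 × 0.0966 + 2.50)/100 = (9.18 + 2.50)/100 = 11.68%

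The shift is about 0.1 to 2.0 percentage points. The exact (Clopper-Pearson) 95% interval for 10 events in 100 is 4.9% to 17.6%, that is, 5.1 points below and 7.6 points above the estimate. Even the top of the assumed range lies well inside it.

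**The case against.** The strongest reply is that Section 3.5 is a narrative summary and not a second eligibility rule. The same sentence paraphrases other criteria loosely. Its reference to hypercoagulable states stands for exclusion 11, which concerns inherited coagulopathy. Its 7-day rule on procoagulant products is counted from Screening, while exclusion 15 counts from enrollment and permits tranexamic acid and platelets. On this reading, recent TEs in Section 3.5 is shorthand for exclusion 7, and sites have one clear rule. This has some force, and most of the safeguard is delivered. It does not remove the conflict: Section 3.6 leans on Section 3.5, and shorthand that promises more than the criteria deliver is what needs correcting.

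Three stronger readings are tempting, and the documents do not support them.

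- *That such patients will present in numbers.* A reader might infer this from Section 3.4.2.2: "Delayed operative management for ischemic conditions could result in necrosis". That passage describes the harm of delaying surgery. Its specific ischemic example is a consequence of small bowel obstruction, not embolism. The non-exhaustive list of expected surgery types in Section 3.4.1 does not name vascular surgery.
- *That the TE rate is materially distorted.* The size rests wholly on assumed inputs. Safety is summarised descriptively, and the protocol sets no TE threshold and no formal comparison with 9.7%.
- *That extension of the original embolus would be counted as a new TE.* Appendix E asks for clear evidence of abrupt occlusion, and the adjudication committee's charter is not in the document. How such a case would be classified cannot be told.

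**Conclusion.** The contradiction stands in the current text. Section 3.5, read with Section 8.2 and Appendix E, makes a patient with an arterial systemic embolism in the last 30 days ineligible; exclusion 7 does not. The gap is limited to visceral emboli and to limb emboli that the undefined peripheral vascular item does not capture.

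This conclusion rests on two readings: that the list in exclusion 7 is closed, which its wording supports, and that severe peripheral vascular disease does not extend to every acute arterial embolus, which is the natural reading but is not settled by a definition.

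The numerical effect cannot be derived from the documents and is probably small against the precision available at about 100 patients. The reason to act is that a stated patient safeguard is incompletely delivered and the document disagrees with itself about who may enter.

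**What to change.** Reconcile Section 3.5 with exclusion 7 in the next amendment, by one of two routes:

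1. Extend exclusion 7, in Section 4.2 and in the synopsis, to cover arterial systemic embolism, as Sections 3.5 and 8.2 together imply.
2. Leave exclusion 7 as it is, and state in Section 3.5 and the benefit-risk text of Section 3.6 that only the TE types listed in exclusion 7 are excluded.

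Which rule applies is for the sponsor to decide. The other items of exclusion 7 and the TE definition used for the endpoint need not change. Forcing one common list for entry and endpoint would unsettle the items on disseminated intravascular coagulation, traumatic coagulopathy and unstable angina without reason.

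The cost is a phrase in two places for the first route, or a sentence in each of two sections for the second. The first route loses a few otherwise eligible patients. The second loses none, but the benefit-risk section must then acknowledge that patients with a recent arterial embolism may be treated.
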